4.2.5.6 St. George's Respiratory Questionnaire (SGRQ)

Changes from baseline in SGRQ total score at Week 52 will be analysed using a similar model (MMRM) for change from baseline in pre-dose/pre-BD FEV₁ (L) in Section 4.2.5.5, with the appropriate baseline value used in the model.

Results will be presented in terms of LSMEANS (with the OBSMARGIN option added), treatment differences in LSMEANS, 95% CI, and p-values for all visits. The results at Week 52 will be of primary interest.

The individual component scores and SGRQ total scores and changes from baseline will be summarised by treatment group and visit.

The cumulative distribution function of absolute changes from baseline in SGRQ total score at Week 52 will be also plotted in a figure.

The proportion of subjects in terms of SGRQ total score response status (improvement, worsening, no change, and not evaluable) at Week 52 will be summarised descriptively by treatment group.

Additional sensitivity analyses to assess the robustness of the repeated measures analysis for SGRQ to missing data are outlined in Appendix 8.2.

Subgroup analyses of the change from baseline in SGRQ total score will be conducted for the subgroup factors listed in Section 3.1.7 based on FAS. The analyses will use the same MMRM model described in Section 4.2.5.5 with additional terms for the subgroup main effect and the interaction among treatment, subgroup and visit. The model of each subgroup will be:

*Change from baseline in SGRQ total score = Treatment group + baseline SGRQ + region (if not subgroup) + prior exacerbation strata (if not subgroup) + visit + treatment*visit + subgroup + treatment* subgroup + subgroup* visit + treatment* subgroup*visit*

Region and prior exacerbation count are not included as a covariate if they are the subgroup factor of interest. Imbalanced subgroups which cause convergence issues may be excluded from the analysis.

Similar outputs will be presented for each subgroup as for the change from baseline in SGRQ total score. The p-value for the interaction term by each treatment group will be presented in the summary tables and a forest plot will present the difference in LSMEANS with 95% CI intervals for each level of the subgroups.

4.2.5.7 Proportion of subjects achieving a decrease of ≥ 4 -points in SGRQ total score at Week 52 (MCID)

The proportion of subjects achieving a MCID of ≥ 4 -units decrease from baseline in SGRQ total score at Week 52 (i.e. responders) in the tezepelumab group will be compared with the proportion in the placebo group using a similar logistic regression model as that used for the proportion of subjects exacerbation-free at Week 52 in Section 4.2.5.2. The baseline SGRQ score will be included as a covariate in this model.

The results of the analysis will be presented as an odds ratio, together with associated 95% CI and 2-sided p-value. The number and percentage of subjects achieving a MCID will also be summarised by treatment group for subjects in the FAS.

As a sensitivity analysis, for subjects who completed the study but have a non-evaluable SGRQ total score change at Week 52 due to missing Week 52 data, the Week 52 assessment will be imputed with the last non-missing post-baseline value (last observation carried forward (LOCF) method) and

responder status will be re-evaluated. A similar logistic regression model as above will be used to compare the proportions of responders as sensitivity analysis.

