4.4 End of Study Definition

For the purpose of Clinical Trial Transparency (CTT) the definition of the end of the study differs under FDA and EU regulatory requirements:

European Union requirements define study completion as the last visit of the last subject for any protocol related activity.

Food and Drug Administration requirements defines two completion dates:

Primary Completion Date – the date that the final participant is examined or receives an intervention for the purposes of final collection of data for the primary outcome measure, whether the clinical study concluded according to the pre-specified protocol or was terminated. In the case of clinical studies with more than one primary outcome measure with

different completion dates, this term refers to the date on which data collection is completed for all of the primary outcomes.

Study Completion Date – the date the final participant is examined or receives an intervention for purposes of final collection of data for the primary and secondary outcome measures and AEs (for example, last participant's last visit), whether the clinical study concludes according to the pre-specified protocol or is terminated.

A subject is considered to have completed the study when he/she has completed his/her last scheduled contact.

See Appendix A 6 for guidelines for the dissemination of study results.

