7.1.1 Procedures for Discontinuation of Study Treatment

Subjects are free to discontinue IP or withdraw from the study at any time without prejudice to further treatment. Discontinuing study treatment is not the same as study withdrawal. In the case of early study withdrawal, the EOT visit should be completed immediately. Subjects who do not wish to have any follow-up contacts as detailed below, will be withdrawn from the study. Procedures to follow for study withdrawal are detailed below in Section 7.3. All withdrawn subjects must return the eDiary device at the EOT visit (and at IPD visit for subjects choosing option 3 below). If the subject decides to withdraw consent, then the reason for this must be recorded separately in the eCRF.

A subject that decides to discontinue IP should always be asked about the reason(s) and the presence of any adverse events. The reason for discontinuing treatment and the date of last IP administration should be recorded in the eCRF. Subjects permanently discontinuing IP administration should be given locally available SoC therapy, at the discretion of the Investigator. However, treatment with marketed or investigational biologics is not allowed until Week 64 even if the subject has discontinued IP. Interaction studies between tezepelumab and other biologics indicated for the treatment of COPD have not been conducted. For additional information regarding pharmacokinetic and pharmacodynamic effects of tezepelumab, please see the Investigator brochure.

All subjects who prematurely discontinue IP should return to the site and complete the procedures described for the premature IP Discontinuation visit (IPD) at 4 weeks (+/-5 days) post last IP administration. Subjects who discontinue treatment should be encouraged to return for all regularly scheduled visits for safety and efficacy assessments.

At the IPD visit the subject will be given three options as to how they will be followed as follows:

- 1. The subject should be encouraged to return for all regular clinic visits and perform all scheduled assessments (excluding IP administration) until the EOT visit at Week 52 (+/-5 days).

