- 2. The subject will be offered follow-up on a monthly basis via telephone calls while continuing eDiary completion (no further procedures will be performed) until the subject completes the EOT visit at Week 52 (+/-5 days). In addition to the PRO assessments that are performed at home, the subject may also complete the other clinic specified PRO assessments (as defined in the SoA 1.1) at home as well.
- 3. If the subject cannot or does not wish to comply with any of the options above, (or any component of them such as only telephone-based visits without completion of the eDiary), the Investigator will only contact the subject at 52 weeks post-randomization. No other study assessments will be performed prior to this contact.

If the subject chooses option 2 or 3, the key information to be collected during the telephone calls are AEs/SAEs, changes in concomitant medication, health care utilization, and COPD exacerbation information.

Subjects who initially choose options 1 or 2 and subsequently cannot or do not wish to comply with the requirements of their option can continue with a less intensive option (i.e., subject initially choosing option 1 can continue with options 2 or 3, subjects initially choosing option 2 can continue with option 3).

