3. If the subject cannot or does not wish to comply with any of the options above, (or any component of them such as only telephone-based visits without completion of the eDiary), the Investigator will only contact the subject at 52 weeks post-randomisation. No other study assessments will be performed prior to this contact.

More details regarding procedures for discontinuation of study treatment are given in Section 7.1.1 of CSP.

The general study design is summarised in Figure 1.

Figure 1 - Study Flow Chart

V1	V2	R/V3	V4-V15	EOT/V16	V17, V18
Week -6	Week -5	Week 0	Week 4-48	Week 52	Week 58, 64
Enrolment	Screening/Run-in	Treatment Phase			Follow-up
Enrolment, Screening/Run-in		Tezepelumab 420 mg, SC every 4 weeks (n=169)			

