4.2 Analysis methods

4.2.1 Subject disposition, demography, and baseline characteristics

Subject disposition will be summarised using the all subjects analysis set. The number of enrolled subjects and those not randomised (and reason) will be summarised. The number and percentage of subjects within each treatment group will be presented by the following categories; randomised, received IP, did not receive IP (and reason), completed treatment, discontinued treatment (and reason), completed study (subjects who completed IP and study, and subjects who discontinued IP but completed study assessments), and discontinued study (including reason). All randomised subjects will be used as the denominator in percentage calculations for the applicable categories above.

Subject recruitment by country and centre will also be summarised for subjects in the FAS.

Disposition will also be provided for the number and percentage of randomised subjects who consented separately to participate in the optional sub-studies (e.g. DNA sampling, sputum and nasal lining fluid/epithelial cells sub studies).

The number of subjects in each of the analysis sets defined in Section 2.1 will be presented.

The number and percentage of subjects, who discontinued IP, but remained in the study will be presented by treatment group and option of follow up (Section 1.2) at each scheduled timepoint.

Kaplan-Meier plots will be produced summarising separately the time (in days) to premature discontinuation of IP and withdrawal from the study. In both cases, subjects without the premature event will be censored at Week 52.

Demographic data such as age, gender, and race will be summarised by treatment group for subjects in the FAS. All subgroups as defined in Section 3.1.7 will be summarised by treatment group for subjects in the FAS. In addition, the screening blood eosinophil category $\geq 150/\mu\text{L}$ will be further categorised as $\geq 150 - 300/\mu\text{L}$, and $\geq 300/\mu\text{L}$ and summarised by treatment group.

Various baseline characteristics will also be summarised for the FAS by treatment group, which include respiratory disease history, subject characteristics (weight, height and BMI), nicotine use and consumption, baseline lung function (pre- and post-BD FEV₁ (L), FEV₁ (% PN), FVC (L), FVC (% PN), and FEV₁/FVC). The number of historic COPD exacerbations will be plotted.

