The method is analogous to the multiple imputation of exacerbation events and the imputation process consists of a sequence of MI steps, where each step is intended to impute missing values at 1 time-point only. This model will assume that some pre-specified subset of subjects who withdraw from the study have correlations with future (unobserved) visits similar to subjects in the placebo arm. As for the exacerbation events, this allows us to assess various deviations from the MAR assumption.

The assumptions that will be used to impute the missing data who withdraw early are as follows:

- (a) MAR: Assumes that the trajectory for subjects who dropped out in each arm is similar to those observed in their own treatment arm
- (b) DRMI: Assumes that the trajectory for subjects in the tezepelumab treatment arm who dropped out for treatment related reasons (according to the same classification as for the DRMI analysis of the primary endpoint) is similar to that of the placebo subjects, whereas the remaining subjects who has dropped out are imputed assuming MAR.

Approach b) can be considered more conservative than the approach for the primary analysis because the assumptions mean that as soon as subjects withdraw for a treatment related reason, they begin to worsen immediately.

The MNAR imputation is achieved by only using appropriate data at each stage of the imputation. Imputation will be done in 2 steps, the non-monotone (intermediate) missing SGRQ total score and FEV₁ values will be imputed first [Markov chain Monte Carlo (MCMC) method is used to partially impute the data using SAS PROC MI] and then the missing value at each visit will be imputed using a sequential regression method (using MONOTONE REG option of SAS PROC MI).

For example, to impute missing values at time t for subjects in the tezepelumab treatment arm, that dropped out due to an AE, include only placebo observations up to and including time t, plus observations from subjects in the tezepelumab arm that dropped out due to an AE, up to and including time t-1. This is done for each visit, one at a time using observed data, and missings just imputed.

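### Two missing-data sensitivity analyses (SGRQ responder LOCF; FEV1/SGRQ DRMI) do not stress subjects who stop IP and stay in the study under follow-up option 3

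*SAP*

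**What the plan says.** **Follow-up after stopping IP.** Protocol 7.1.1 offers three options at the IPD visit. Under option 3, "the Investigator will only contact the subject at 52 weeks post-randomization", and SAP 1.2 repeats that "No other study assessments will be performed prior to this contact". The telephone contact collects adverse events, medication changes, health care use and exacerbations. Option 3 subjects hand back the eDiary at IPD, and SGRQ is completed on the eDiary (SAP 3.2.2.6).

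**Withdrawal and completion.** Only those who refuse every option leave the study: "Subjects who do not wish to have any follow-up contacts as detailed below, will be withdrawn from the study". Protocol 4.4 states: "A subject is considered to have completed the study when he/she has completed his/her last scheduled contact". SAP 4.2.1 is worded differently. Its completers include "subjects who discontinued IP but completed study assessments", and it separately tabulates subjects "who discontinued IP, but remained in the study will be presented by treatment group and option of follow up". It does not say whether option 3 counts as completion.

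**Responder analysis.** In the main analysis a missing Week 52 SGRQ change makes the subject a non-responder (SAP 3.2.2.6). The sensitivity analysis in SAP 4.2.5.7 uses LOCF "for subjects who completed the study but have a non-evaluable SGRQ total score change at Week 52 due to missing Week 52 data", taking the most recent post-baseline score available.

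**DRMI for FEV1 and SGRQ.** SAP 8.2 assumes that "some pre-specified subset of subjects who withdraw from the study have correlations with future (unobserved) visits similar to subjects in the placebo arm". The table in SAP 8.3 likewise names withdrawal from the study as the event assumed to be MNAR. The reasons are those of Table 4 (withdrawal). Table 5 (IP discontinuation) serves only the exacerbation counts under the supplemental estimand, in an analysis that is optional.

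**The concern.** Both analyses are there to test secondary endpoints against missing data. Option 3 subjects are among those for whom the test matters most: they stopped the drug, and their off-drug FEV1 and SGRQ were not measured.

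The LOCF rule relaxes the main rule for these subjects. It replaces non-response with a score usually taken within about a month of the last dose, possibly most of a year earlier. The DRMI rule passes them by, because its trigger is leaving the study rather than stopping IP. That trigger suits exacerbations, which the option 3 contact still collects. It does not carry over to FEV1 and SGRQ, which that contact does not collect.

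Agreement between these analyses and the main ones could then be read as robustness when this group had not been tested.

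**Working it through.** The plan gives no figure for this point, so there is none to reproduce. The check is date arithmetic plus an illustration of size.

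**Inputs**
- Target day = 7 × week + 1. This matches SAP Table 1: Week 12 = Day 85, Week 48 = Day 337, Week 52 = Day 365.
- SGRQ schedule (protocol Table 2): Weeks 0, 12, 24, 36, 48 and 52, and the IPD visit.
- IPD visit: 28 days (±5) after the last dose (protocol 7.1.1).
- On-treatment limit: last dose + 33 days (SAP 2.1.5).
- Week 52 window: Days 351–385 (SAP Table 1).

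**Is the IPD score on-treatment?** The latest in-window IPD visit is 28 + 5 = 33 days after the last dose, which equals the limit. An in-window IPD score is therefore always on-treatment. A subject who moves from option 1 or 2 down to option 3 may have a later, off-treatment last score.

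**How far is it carried?** Carry in weeks = (365 − IPD day) / 7, with IPD day = last-dose day + 28.

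| Last dose | IPD day | Carry to Day 365 |
|---|---|---|
| Week 0 | 29 | 336/7 = 48 weeks |
| Week 4 | 57 | 308/7 = 44 weeks |
| Week 8 | 85 | 280/7 = 40 weeks |
| Week 12 | 113 | 252/7 = 36 weeks |
| Week 44 | 337 | 28/7 = 4 weeks |

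With the ±5-day window the maximum runs from 47.3 to 48.7 weeks. A subject who misses only Week 52 would instead have a Week 48 score about 4 weeks old.

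**Contrast with a withdrawal.** A subject who withdraws at Week 49 (Day 7 × 49 + 1 = 344) and completes the immediate EOT visit has a score (365 − 344)/7 = 3 weeks old. Day 344 is before the Week 52 window and the subject is not a completer, so nothing is carried and the subject stays a non-responder. An option 3 subject with a 48-week-old score can become a responder.

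**DRMI route.** Take a tezepelumab subject who stops for an adverse event, takes option 3 and answers the Week 52 contact.
1. FEV1 and SGRQ after IPD are missing in a monotone pattern, so the sequential regression step applies.
2. The subject has not withdrawn, so no Table 4 reason exists.
3. Table 5 is not invoked for FEV1 or SGRQ.
4. Under the trigger wording in SAP 8.2 and 8.3, the values are imputed under MAR from the tezepelumab arm.

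**Size of the LOCF shift.** Shift in an arm's response rate, relative to non-responder imputation = share in option 3 × proportion of these who are responders at their last score. The documents give neither figure, so both ranges are assumptions.

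| Option 3 share | Of 169 | 30% responders | 50% responders |
|---|---|---|---|
| 2% | 3.4 | 0.6 points | 1.0 points |
| 5% | 8.5 | 1.5 points | 2.5 points |
| 10% | 16.9 | 3.0 points | 5.0 points |

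The shift in the between-arm difference is one arm's value minus the other's. It is zero if the arms match. Across these ranges it is at most 5.0 − 0.6 = 4.4 points, in either direction.

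**The case against.** **Completer status is inferred.** The SAP 4.2.1 wording about completing study assessments could be read to exclude option 3, and SAP 4.2.5.7 does not define completion. This stands: a reader should not take it that the documents state option 3 subjects are completers. The inference is still the natural one, because these subjects are not withdrawn and, for follow-up to Week 52, that contact is their last.

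**DRMI may reach further.** A later paragraph of SAP 8.2 assigns MAR to tezepelumab values whose absence is not due to adverse events. That is keyed to the reason for missingness, not to withdrawal. An option 3 subject who later withdraws or is lost also falls under Table 4. So it cannot be said that DRMI never treats these subjects as drop-outs. The wider reading, however, conflicts with the trigger stated elsewhere in 8.2 and in 8.3.

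**Own-arm imputation is not the most favourable value.** The 8.3 table describes the MAR imputation as drawing on off-treatment data from the same arm. Under the primary estimand, own-arm data include off-treatment values from option 1, and possibly home SGRQ from option 2. This stands, though it still leaves out the placebo trajectory that DRMI is meant to apply.

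**The consequences are limited.** The main responder analysis already uses non-responder imputation, LOCF applies to both arms, p-values beyond the primary endpoint are nominal (SAP 4.1.2), and discontinuers are tabulated by arm and follow-up option. Supplemental-estimand analyses of FEV1 and SGRQ also stop at IP discontinuation. All true. These points limit the weight of the issue, but do not make the two analyses a test of this group.

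**Conclusion.** The point holds as a should-fix matter for two sensitivity analyses of secondary endpoints. Followed as written, the LOCF rule can carry an option 3 subject's IPD score 4 to 48 weeks to Week 52, and the DRMI trigger leaves such a subject under own-arm MAR.

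This rests on reading completion through protocol 4.4, and on the withdrawal wording of SAP 8.2 and 8.3 prevailing over the adverse-event wording in 8.2. The LOCF effect, 0.6 to 5.0 percentage points in an arm, rests on assumed shares and response rates.

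A reader might infer that the plan favours tezepelumab, or that the main responder result is biased. The documents support neither: the direction depends on which arm has more option 3 subjects with a favourable last score, and the main analysis does not use LOCF.

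**What to change.** **SAP 4.2.5.7.** Carry forward only an SGRQ score from the Week 48 window; everyone else with a missing Week 52 score stays a non-responder. State which window is meant. The Table 1 window, Days 323–350, limits the carry to (365 − 323)/7 = 6 weeks. The SGRQ-specific window from the half-way rule in SAP 3.1.5, Days 295–350, limits it to (365 − 295)/7 = 10 weeks. If the completer condition is kept, say how option 3 is classified. Restricting LOCF further to subjects still on IP would be a preference, not a requirement, under an estimand that uses data regardless of discontinuation.

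**SAP 8.2 (continuous endpoints) and the 8.3 table.** Extend the DRMI trigger to monotone missing FEV1 and SGRQ after IP discontinuation in subjects who stay in the study, using the Table 5 reasons. Leave intermittent gaps to the existing non-monotone step. Align the adverse-event wording in 8.2 with the trigger.

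**Cost.** SAP wording and a little programming. The on/off-treatment flag (SAP 3.1.5), the discontinuation reason and the follow-up option (SAP 4.2.1) are already planned. The sensitivity results may look less favourable.

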4.2.5.8 COPD assessment tool (CAT)

The CAT total scores and changes from baseline will be summarised by treatment group and visit.

Change from baseline in CAT score through Week 52 will be analysed using a similar model (MMRM) as for the change from baseline in pre-dose/pre-BD FEV₁ (L) described in Section 4.2.5.5. Results will be presented in terms of LSMEANS (with the OBSMARGIN option added), treatment differences in LSMEANS, 95% CI, and p-values for all visits.

4.2.5.9 Additional supportive endpoints to secondary

The proportion of subjects with ≥ 1 severe COPD exacerbation over 52-weeks treatment will be analysed similarly to the proportion of subjects exacerbation free at Week 52 in Section 4.2.5.2.

4.2.6 Exploratory outcome variables

All continuous exploratory endpoints will be summarised descriptively and analysed under a MAR assumption using an MMRM model analogous to that specified for the secondary endpoints in Section 4.2.5.5 and handling intercurrent events as per the primary estimand.

The following is proposed for the exploratory endpoints:

- Change from baseline and percent change from baseline in blood eosinophil and neutrophil levels summarised descriptively
- Change from baseline in post-BD FEV₁ (L) analysed using MMRM and summarised descriptively
- Change from baseline in E-RSTM: COPD total score and domain scores analysed using MMRM and summarised descriptively
- Change from baseline in FENO analysed using MMRM and summarised descriptively

Results of MMRM analyses will be presented in terms of LSMEANS (with the OBSMARGIN option added), treatment differences in LSMEANS, 95% CI, and p-values for all visits.

Summary statistics of the EXACT-PRO event frequency, duration, and severity will be produced by treatment group.

Annual rate of EXACT-PRO defined exacerbation will be analysed using the method described for the primary analysis in Section 4.2.4.1 for subjects in the full analysis set. 95% CI will be presented for annual exacerbation rate, absolute difference, and the rate ratio.

All time to event exploratory endpoints will be analysed by using the same Cox proportional hazard model as in Section 4.2.5.1, and will be displayed graphically using a Kaplan-Meier plot.

This analysis includes the following endpoints:

- Time to first COPDCompEx event over 12-weeks
- Time to CID event over 52 weeks-treatment

COPDCompEx rates in the tezepelumab group will be compared to those seen in the placebo group using a negative binomial model, similarly to the primary analysis under the primary estimand in Section 4.2.4.1. The response variable in the model will be the number of COPDCompEx events experienced by a subject over the first 12 weeks of treatment period as well as over the entire 52 week treatment period. Treatment, region, and number of exacerbations at randomization as recorded in IWRS (2, ≥ 3) will be included as covariates in this model. The logarithm of subject's time at risk (in years) for a COPDCompEx event will be used as an offset variable in the model, to adjust for subjects having different follow-up times during which the events occur (noting that the maximum follow up time is to Visit 6 (week 12) and Visit 16 (and Week 52)). For all further derivation details, see Section 3.2.3.1. The estimated treatment difference from placebo (i.e. the absolute difference between tezepelumab and placebo, and the rate ratio of tezepelumab versus placebo), corresponding 95% CIs, and 2-sided p-value for the ratio will be presented. Descriptive summaries of the COPDCompEx events will also be presented. A bar chart showing the percentage of subjects by number of COPDCompEx events over 12 weeks and 52 weeks will also be presented.

The annual rate of each resource utilisation through Week 52 in the tezepelumab group will be compared to that seen in the placebo group using a negative binomial model, similarly to the primary analysis under the primary estimand in Section 4.2.4.1. The response variable in the model will be the number of times of each COPD specific resource utilisation items as listed in Section 3.2.3.7. The logarithm of the subject's corresponding follow-up time as defined in Section 3.2.1.1 will be used as an offset variable in the model to adjust for subjects having different exposure times during which the events occur. The estimated treatment difference from placebo (i.e. the absolute difference between tezepelumab and placebo, and the rate ratio of tezepelumab versus placebo), corresponding 95% CIs, and 2-sided p-value for the ratio will be presented. The number and percentage of subjects with COPD specific resource utilisation, specified in Section 3.2.3.7, and overall annual rate during the treatment period will be summarised by treatment group for subjects in the FAS. The total number of days/times and annual rate of each specific resource utilisation at a subject level will be summarised by descriptive statistics.

Sensitivity and subgroup analyses will not be performed on exploratory endpoints.

